The primary purpose of this study is to assess the efficacy of larval debridement therapy (LDT) with bagged, sterilized, live, medicinal blow fly (*Lucilia sericata*) larvae (or "BioBags") versus bedside sharp debridement in removing harmful bacteria, biofilm and necrotic tissue from chronic wounds to promote wound healing. Characteristics associated with chronic wound environments will be evaluated through analysis of samples of tissue taken from wound beds before and after both types of debridement. One hundred and forty patients \geq 21 years of age with an open, full thickness wound which is healing by secondary intention (of greater than 8 weeks duration and requires debridement) will be invited to participate. This recruitment number accounts for estimated 10% attrition rate, so final sample number is anticipated to be 128 subjects (64 in each arm). Samples of wound bed tissue and slough tissue (if present) will be collected on Days 0, 4 and 8 or prior to and after each larval debridement intervention or sharp debridement (control). Photos will be taken of the wound bed on Days 0, 4 and 8 or just prior to and after each debridement method. A randomized sampling procedure will place individuals into one of two groups: The intervention group will receive larval debridement therapy once every 4 days for 2 applications (with saline moistened gauze as cover dressing changed daily) and the control group will receive sharp debridement therapy every 7 days for 2 debridements (with wound gel dressing changed daily).

The wound and wound environment will be characterized by assessing wound Matrix Metalloproteinases (MMPs), inflammatory cytokines and the presence of total bacteria, planktonic (free floating) bacteria, and biofilm (sessile) bacteria. Clinicians will be asked to grade the amount of non-viable tissue apparent in the wound bed, appearance of any signs of infection and overall visual appearance of the wound at each visit. Wound size will also be assessed. Subjects will be asked to rate their wound related pain level at each visit before and after the debridement method is applied. Subjects, caregivers and clinicians will be asked to complete a short survey to self-report their perceptions of each method of debridement. Data will be analyzed using bivariate and multivariate methods.

4. **Background:**

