information). The clinicians will also be asked to make a Recruitment Brochure available to potentially eligible patients (those with lower extremity or diabetic foot ulcers over 8 weeks duration). In addition, study flyers will be sent to select VA wound and podiatry offices in the NF/SG VHS. Providers will be asked to contact study team if any patient is willing to hear about the study. If the patient is willing to hear about the study, they may contact a study team member from the contact number on the recruitment brochure or the provider can let the patient know when the research team member is scheduled to be in the provider clinic office and the patient may talk directly to the research study team member for more information. If patients call a research team member, they will have their questions answered but will not be screened over the phone. They will be scheduled to come into the provider office to discuss the study with a research team member and review informed consent. Members of the research study team will review the informed consent with the patient and enroll the subject if they agree to participate. Wound clinicians will not be asked to consent subjects, or to provide a list of patients or appointment times to research team. However, the subject's wound providers (clinicians) will be the ones to perform the sample collection and apply the LDT or bedside sharp debridement. The sample also includes one available caregiver of the patient (non-professional) to answer the caregiver surveys if willing, and the wound care providers, who will be asked to answer the clinician survey regarding perceptions of debridement methods.

Sample Size Power Analysis: Power analysis is based on the patient sample and the primary study aim of comparing debridement methods on clinical effectiveness. The POWER procedure in SAS version 9.2 (Cary, N.C.) was used to conduct the power analysis. Assuming a Type I error rate of .05 and two-sided testing, a sample of 64 is needed in each group to detect a medium effect size of .50 with at least 80% power. This magnitude of effect is considered clinically significant.

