Exclusion criteria: (1) Cognitive impairment that would interfere with patient signing their own Informed Consent; (2) Individuals on active anticoagulant therapy with most recent (within last week) PT/INR (international normalized ratio of prothrombin time) > 3.0, or other significant bleeding risk; (3) Active immune suppression just prior to or during study (on systemic corticosteroids* within 7 days prior, or chemotherapy for cancer or RA treatment within 4 weeks prior to study, or with diagnosis of HIV/AIDS) - *Nasal steroid sprays will not be excluded; (4) Active systemic antibiotics is an exclusion; (5) Absent dorsalis pedis pulses and Ankle Brachial Index (ABI) < 0.5 is an exclusion (indicates critical limb ischemia). Other possible reasons participants could be removed from this study include: transfers to other non-study participating facilities, participant is unable to tolerate tissue sampling even with local anesthesia, at the discretion of the provider for clinical reasons, and/or inability to comply with scheduled research visits. Furthermore, if the participant has significant wound healing so that sampling is not possible after the initial sampling, they will be removed from the study.

Human Subjects Involvement and Characteristics: After signing informed consent, participants and their (non-professional) caregivers will be randomly assigned to one of two study arms: (1) Larval Debridement Therapy (LDT) or (2) Bedside Sharp Debridement (control). The intervention group, or LDT participants, will undergo LDT every 4 days for 2 applications as the main method of debridement strategy. They will have wound samples collected before the initial larvae are applied after 4 days of larval therapy and after 8 days of larval therapy. They will also both be asked to complete a short paper survey on Days 0, 4 and 8. The subject's wound clinician will also be asked to complete (if willing) a similar survey (only one round of surveys per consented wound clinician) at Day 0 and Day 8 and 3 months later or at completion of study regarding perceptions of wound debridement therapy.

The control group (bedside sharp debridement) will receive sharp debridement of their wounds 7 days apart x 2 sharp debridements and also have wound samples collected before the initial sharp debridement (Day 0), 4 days after the initial sharp debridement (Day 4), then eight days after initial sharp debridement, which will be 24 hours after the second sharp debridement (Day 8).

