Measurement of IL6. Using techniques such as ELISA and fluorescence resonance energy transfer (FRET) assay methodology, the levels of active IL6 will be calculated and reported.

Methods for Data Collection & Data Management

Variable	Significance	Sampling time	Source	Specific Aim
Age	Demographic	Baseline	EHR	n/a
ABI	Exclusion criterion	Baseline - enrollment	ABI done after ICF	n/a
% nonviable wound tissue	Appearance of wound bed	Baseline Day 0 and Day 8	Provider assessment	Aim 1
Quantitative Cultures (planktonic and biofilm)	Microbial identification	Day 0 (pre-test), + Day 4 and Day 8	Wound samples	Aim 1
Wound Size in cm ² (volume: L x W x D)	Descriptive	Baseline Day 0 and Day 8	Wound measurements	Aim 2
Interleukin 6	Marker of inflammation	Day 0 (pre-test), + Day 4 and Day 8	Wound sample (fluid and/or tissue)	Aim 2
Matrix metalloproteinases (MMP-2 and 9 equivalent)	Elevated MMPs associated with non-healing wounds	Day 0 (pre-test), + Day 4 and Day 8	Wound sample (fluid and/or tissue)	Aim 2
Perceptions of therapy	Perceptions of debridement	Day 0 (pre-test) + Day 8	Patient, Caregiver & Clinician Surveys	Aim 3

Survey Methods

Subjects will be asked to complete a paper survey at Day 0, Day 4 and Day 8 of the study, querying the patient's perceptions of: wound pain, satisfaction with most recent/current wound care method, ease of

care, effectiveness of most recent wound treatment, aesthetics of current wound treatment and toward sharp debridement and maggots for wound care.

Caregivers and wound clinical providers will be asked to complete a paper survey at Day 0 and Day 8 of the study (if wound clinician is caring for more than one study subject, they will be asked to complete a survey at day 0 of first subject, day 8 of first subject and 3 months later or at completion of the study for each type of debridement), querying them about their perceptions of what the patient's experience was regarding the most recent wound debridement methods as well as satisfaction with most recent/current wound care method, ease of care, effectiveness of most recent wound treatment, aesthetics of most current wound treatment and toward sharp debridement and maggots for wound care.

Data Analysis

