Data will be summarized with descriptive statistics. Data will be checked for implausible values, missingness, and distributional form. Data transformations will be made as necessary to achieve normality. To address Specific Aim 1 (comparing the clinical effectiveness of a self-contained larval debridement therapy with a bedside sharp debridement therapy), the numeric outcome measures of changes (post minus pre) in percent of non-viable tissue and bacterial biofilm will be analyzed using independent samples t-tests. To address Specific Aim 2 (comparing wound characteristics of larval debridement and bedside sharp debridement therapies) over time, longitudinal generalized mixed models (GLMMs) will be used with the dependent repeated measures being wound characteristics (e.g., inflammatory markers, wound size) and the independent variable of group assignment (larval versus sharp debridement). To address Specific Aim 3 (investigating patient, caregiver, and clinician perceptions of larval therapy dressings and bedside sharp debridement using self-reported assessments, independent samples t-tests will be used to analyze data measured at the interval level, Wilcoxon rank sum tests will be used to analyze data measured at the ordinal level, and chi-square tests (or Fisher exact tests in the case of data sparseness) will be used to analyze categorical data. All hypotheses testing will be two-sided using a level of significance of .05. Data will be analyzed as "intent to treat." SAS version 9.2 (Cary, N.C.) will be used for all analysis.

Data and Safety Monitoring Plan

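### Aim 3 rates pain and perceptions repeatedly, but its between-arm tests name no visit, change score or baseline adjustment

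*Combined protocol and SAP*

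**What the plan says.** Specific Aim 3 covers how patients, caregivers and clinicians regard the two methods, and it includes wound pain. This point concerns the patient and caregiver ratings.

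Collection is repeated. Survey Methods states: "Subjects will be asked to complete a paper survey at Day 0, Day 4 and Day 8 of the study". Human Subjects Involvement and Characteristics, in the larval-arm text, states: "They will also both be asked to complete a short paper survey on Days 0, 4 and 8". The opening summary adds: "Subjects will be asked to rate their wound related pain level at each visit before and after the debridement method is applied". Survey Methods gives caregivers a survey at Days 0 and 8.

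The sections do not agree on Day 4. The sampling timeline under Study procedures lists only a pain survey that day. The variable table under Methods for Data Collection & Data Management lists perceptions at Days 0 and 8 only.

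For the Aim 3 analysis, Data Analysis states: "independent samples t-tests will be used to analyze data measured at the interval level". Ordinal items get Wilcoxon rank sum tests, and categorical items get chi-square or Fisher tests. Nothing says which visit enters, whether a change is taken, or whether Day 0 is used. The other two aims are more definite in the same paragraph. Aim 1 analyses a before-to-after change, and for Aim 2 "longitudinal generalized mixed models (GLMMs) will be used with the dependent repeated measures being wound characteristics". The error rule is general: "All hypotheses testing will be two-sided using a level of significance of .05".

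**The concern.** An independent-samples test needs one value per person. Each patient supplies two or three dated ratings per item, and possibly more for pain. A statistician working from the text could not tell which value to use.

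The choice is not neutral, because the arms sit at different points in treatment at each visit. On Day 4 the larval arm has just had its first bag removed, while controls are four days past sharp debridement. On Day 8 controls are 24 hours past their second sharp debridement. The between-arm difference in pain could therefore depend on the visit. If the visit is open, it can be settled once results are known.

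Separately, a test on Day 8 alone ignores a pre-treatment rating that is already being collected. Aim 3 carries the trial's conclusions on acceptability and pain, so both matters bear on what can be claimed there.

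**Working it through.** **1. Ratings available per item**

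| Source | Day 0 | Day 4 | Day 8 |
|---|---|---|---|
| Opening summary | pain, before and after debridement | same | same |
| Human Subjects Involvement | survey | survey | survey |
| Survey Methods, patients | survey | survey | survey |
| Survey Methods, caregivers | survey | none | survey |
| Sampling timeline | surveys | pain survey only | surveys |
| Variable table, perceptions | yes | not listed | yes |

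The variable table has no separate pain row. Patient pain at three visits is supported by all the other sources. Other perceptions are rated at Days 0 and 8 on every reading, and at Day 4 on some.

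**2. The plan's own figure.** Sample Size Power Analysis states that "a sample of 64 is needed in each group to detect a medium effect size of .50 with at least 80% power". A two-sample t-test at effect 0.50, two-sided .05 and 80% power needs 63.77, so 64 per group. Power at 64 is 0.801, so the figure reproduces. It was set for the primary aim and serves here only as a yardstick.

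**3. Leaving the visit open.** This step applies to items rated at both Day 4 and Day 8. With two separate .05 tests and no true effect, the chance of at least one false positive is 1 − 0.95² = 9.75% if the ratings are uncorrelated. The documents give no within-person correlation, so 0.3 to 0.7 is assumed, equal across visits. Simulation with 64 per arm and 40,000 replicates per correlation gives 9.4%, 8.9% and 8.2% at 0.3, 0.5 and 0.7.

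**4. Leaving Day 0 unused.** This step applies to interval items. Take the Day 8 variance as 1 and r as the Day 0 to Day 8 correlation. Then:

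- Day 8 alone has variance 1.
- Day 8 minus Day 0 has variance 2(1 − r).
- Day 8 adjusted for Day 0 has variance 1 − r².

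Power is from the t-test with 64 per arm and effect 0.50/√variance:

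| r | Day 8 alone | Change score | Day 8 adjusted for Day 0 |
|---|---|---|---|
| 0.3 | 1.00; 80% | 1.40; 66% | 0.91; 84% |
| 0.5 | 1.00; 80% | 1.00; 80% | 0.75; 90% |
| 0.7 | 1.00; 80% | 0.60; 95% | 0.51; 98% |

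In sample-size terms, 64/(1 − r²) means that 64 per arm would act like about 70, 85 or 125. The change score never beats adjustment, because 2(1 − r) − (1 − r²) = (1 − r)², which cannot be negative. At r = 0.1 the variance falls by only 1% (1 − 0.99).

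**The case against.** The strongest reply is that the named tests are not wrong in themselves. Aim 1 applies the same t-test to a before-to-after change, and the variable table pairs Day 0 with Day 8 for perceptions, so a change score may be what was meant. That would be one value per person and a valid test. This stands as far as it goes. But the change is not stated for Aim 3, it would leave the Day 4 pain rating unused, and it is never more precise than adjustment for Day 0.

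A reader might infer that the visits will be stacked as if they were independent patients. Stacking three visits would give a type I error of about 12% to 21% at the same correlations. No section proposes this, so those figures describe a hypothetical analysis and are no part of the finding. Nor do the documents show that ratings will be split by visit or discarded; the text merely allows it.

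Three further limits stand:

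- Three visits is contradicted for items other than pain, so the Day 4 and Day 8 false-positive figure is firm only for pain.
- The correlation is assumed. It may be low for perceptions, since the survey asks about the latest or current wound care, and on Day 0 that can mean care before the study.
- The survey forms are in appendices outside the text reviewed, so which items are interval and which ordinal is unknown.

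A mixed model also adds little for an item with a single post-baseline rating. With Day 0 as covariate it reduces to ordinary covariate adjustment.

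**Conclusion.** The point holds as under-specification with a cheap improvement available, not as a demonstrated wrong test. Aim 3 names no visit, change score or baseline term for ratings collected at two or three visits. For pain, choosing between Days 4 and 8 after the fact carries about an 8% to 10% false-positive chance in place of 5%. The same applies to any other item found to be rated at both visits. For interval items, using Day 0 as a covariate would lift power at 0.5 SD from 80% to about 84%, 90% or 98%.

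These sizes rest on an assumed correlation of 0.3 to 0.7 and on 64 per arm, and the power gain shrinks at lower correlations. No power is stated for Aim 3, and neither the sample size nor the Aim 1 comparison is affected.

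**What to change.** In Data Analysis, for Aim 3:

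- Name one between-arm contrast per repeated item, for example Day 8, adjusted for the same person's pre-treatment Day 0 rating. Use ANCOVA for interval items and a proportional-odds model for ordinal items.
- For patient pain, which has two post-baseline visits, use the longitudinal mixed model already planned for Aim 2, with visit and arm-by-visit terms. Make Day 4 supportive.
- State which pain rating enters, before or after debridement. The Day 0 covariate must be the rating taken before treatment. By the timeline the control arm is debrided on Days 0 and 7, so before and after need defining for its Day 4 and Day 8 ratings.
- Keep the t, rank sum and chi-square or Fisher tests for items asked once.

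Reconcile the Day 4 survey content across Human Subjects Involvement and Characteristics, the sampling timeline, the variable table and Survey Methods.

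The cost is a few sentences and slightly more programming, with no new patients, visits or data. The drawback is that ordinal models are less familiar than rank tests.

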To compare the clinical effectiveness of a self-contained bagged larval debridement therapy (intervention) (BioBag) with bedside sharp debridement (control). The following comparisons will be made: 1) The visual reduction of non-viable tissue in the wound bed of chronic full-thickness lower extremity or diabetic foot ulcers, and 2) The reduction in colony forming units (CFU) of bacterial biofilm in samples taken from the wound bed.

Specific Aim 2

To compare wound characteristics (e.g., inflammatory markers, wound size) in the intervention group (BioBag therapy) and control group (Sharp debridement) over time.

Specific Aim 3

To investigate patient, caregiver and clinician perceptions of larval therapy dressings and bedside sharp debridement using measures of self-reported aesthetics, ease of use, and wound pain.

6. Research Plan:

Research design and methods

Design: A repeated measures, randomized control trial experimental design will be used for this study. Subjects will serve as their own control, in addition to a control group. Initial wound samples will be followed by two subsequent repeated wound samplings approximately four days apart. Informed consent will be obtained prior to all procedures, photo consents will also be obtained for wound photos.

Veteran Site: North Florida South Georgia Veterans Health System

Setting, Sample: A target goal final sample size of one hundred twenty eight adults from the North Florida South Georgia VHS will be recruited (total recruited number anticipated to be ~140 allowing for 10% attrition). Including target of 128 Caregivers and 6 Providers, and accounting for 12 caregivers lost to follow up or 10 subjects who fail screening, the total study recruitment population is 296. Wound providers and clinicians who care for lower extremity or diabetic foot ulcers will be provided with a "Provider Study Flyer" which gives a brief description of the study with inclusion/exclusion criteria listed (to remind the Provider to approach potentially eligible patients with Research Team Contact

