X post-measure (**sample 2**); Pain survey; photos
Apply larvae bag 2
- Day 8 - **X** final measures (**sample 3**); surveys; photos

SD group

- Day 0 - **X** pre-measures (**sample 1**); surveys; photos
Sharp Debridement 1
- Day 4 - **X** post measures (**sample 2**); pain survey; Wound photos
- Day 7 - Sharp debridement 2 & photos
- Day 8 - **X** final measures (**sample 3**); surveys; photos

Data Collection & Data Management

Measurement of bacterial colonization. A microbiological assessment of the wound samples will be performed. Samples will be measured for both planktonic (single) bacteria and biofilm bacteria by standard clinical microbiology techniques with serial dilution and plating on complete agar medium

plates. Colony forming units (CFUs) will be measured after approximately 24 hours of culture under standard laboratory conditions. Levels of planktonic bacteria and biofilm bacteria will be compared within each sample and chronologically within each patient. Photos will be reviewed by blinded wound clinicians and rated on amount of necrotic tissue present visually in wound bed at each sampling time (reported on scale 0 – 10 based on 0%, 1 = 10% or less, etc.). Data collected from human subject's electronic health record will include characteristics such as wound etiology, wound location/duration, wound treatments, wound photos, wound progress notes, age, gender, comorbid conditions, pertinent laboratory values and medical history. This data will be conducted only by trained research team members designated in the IRB approved study protocol over the duration of the study.

Only de-identified pertinent information per subject sample such as age of subject, visit number (Day 0, 4, 8), location of wound, duration of wound, co-morbid conditions, medications and current wound treatments will be shared with the investigational laboratories or their personnel. Only the PI, site PI, Co-Investigators, and study coordinator(s) will have access to the subject PHI and study folders. UF lab has agreed to destroy any remaining samples at the conclusion of the current study.

Measurement of MMPs. Using techniques such as ELISA or fluorescence resonance energy transfer (FRET) assay methodology, the levels of active MMPs (or measures of MMP activity) will be calculated and expressed as pg/ml of wound fluid and pg/mg protein.

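### Aim 1, on which the sample size rests, has two unranked outcomes each tested at .05, no rule for combining them, and no fixed post day for either

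*Combined protocol and SAP*

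**What the plan says.** The Sample Size Power Analysis, given once for each site, ties the calculation to one aim: "Power analysis is based on the patient sample and the primary study aim of comparing debridement methods on clinical effectiveness". On that basis "a sample of 64 is needed in each group to detect a medium effect size of .50 with at least 80% power", with a two-sided Type I error of .05. It names no outcome.

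Section 5, Specific Aim 1, gives that aim two comparisons, numbered but not ranked. The first begins: "The following comparisons will be made: 1) The visual reduction of non-viable tissue in the wound bed". The second is: "The reduction in colony forming units (CFU) of bacterial biofilm in samples taken from the wound bed". The opening study summary (before section 4) also puts them side by side, assessing larval therapy "versus bedside sharp debridement in removing harmful bacteria, biofilm and necrotic tissue from chronic wounds to promote wound healing".

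For Aim 1, Data Analysis says that "the numeric outcome measures of changes (post minus pre) in percent of non-viable tissue and bacterial biofilm will be analyzed using independent samples t-tests". For every test it says: "All hypotheses testing will be two-sided using a level of significance of .05". It gives no day for 'post' and, for tissue, no measurement source.

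Other sections bear on day and source:

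- **Biofilm cultures.** The table under Methods for Data Collection & Data Management lists Days 0, 4 and 8.
- **Tissue, provider assessment.** The same table lists Days 0 and 8 only. The opening summary has clinicians grade it at every visit.
- **Tissue, photographs.** Data Collection & Data Management has blinded clinicians rate the photos at each sampling time.
- **Labels.** The sampling timeframe for the sharp debridement group describes Day 4 as "post measures (sample 2); pain survey; Wound photos" and calls the Day 8 measures final. The larval group's entries use the same labels.
- **Control sampling.** Human Subjects Involvement and Characteristics (both sites) places the Day 4 sample four days after the first sharp debridement, and the Day 8 sample 24 hours after the second.

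**The concern.** One error rate and one power figure are stated for one aim, but the aim is answered by two tests. Nothing says whether a conclusion that larval therapy is more clinically effective needs one significant result or both. The stated 5% and 80% describe a single test and carry over to Aim 1 only once that rule is known.

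The post day adds a second gap. Two analysts who both follow Data Analysis could test different quantities, and the choice is not neutral: on Day 8 the control wound has been sharply debrided the day before, while on Day 4 it has not been debrided for four days. If these choices are left until results are visible, a reader of the report cannot tell which test was the planned one.

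**Working it through.** **1. The plan's own figure.** Inputs from the Sample Size Power Analysis: d = 0.50, two-sided alpha .05, 64 per arm. For a two-sample t-test the noncentrality is 0.5 × √(64/2) = 2.83 with 126 df, which gives power of 80.1%. Solving for 80% gives 63.77, rounded up to 64. The figure reproduces, for one test of one outcome.

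**2. Two separate claims.** Each test has 5% error and 80.1% power. Nothing changes.

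**3. One conclusion, either outcome suffices.** With independent outcomes, the two-sided error is 1 − 0.95² = 9.75%. Counting only false results in favour of larval therapy, it is 1 − 0.975² = 4.9%, against a nominal 2.5%.

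**4. One conclusion, both outcomes required.** Error stays within 5%. With independent outcomes and d = 0.50 on each, power is 0.801² = 64%.

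The documents give no correlation between the outcomes, so a range is assumed. The correlated rows come from simulating pairs of t statistics with 126 df (1,000,000 trials).

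| Assumed correlation | Two-sided error, either suffices | False larval win, either suffices | Power, both required |
|---|---|---|---|
| 0 | 9.75% | 4.9% | 64% |
| 0.5 | 9.1% | 4.6% | 69% |
| 0.9 | 7.0% | 3.5% | 75% |

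**5. What 'post minus pre' could mean.**

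| Outcome and source | Day 4 minus Day 0 | Day 8 minus Day 0 |
|---|---|---|
| Biofilm, culture | yes (table) | yes (table) |
| Tissue, provider | yes by the opening summary, no by the table | yes |
| Tissue, blinded photo | yes (each sampling time) | yes |

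Biofilm has two candidate contrasts. Tissue has three, or four if the summary's rule for provider grading applies. Taking 'post' from the schedule label points to Day 4, but the table then has no provider tissue value. Taking Day 8 from the table conflicts with the schedule, which calls Day 8 final.

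**6. Figures for the remedies.** At alpha .025, 64 per arm and d = 0.50 give 71% power; 80% would need 78 per arm.

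For adjustment on Day 0, assume equal SD σ before and after and pre-post correlation ρ. The change score has SD σ√(2(1−ρ)) and the adjusted comparison has residual SD σ√(1−ρ²), a ratio of √((1+ρ)/2). If d = 0.50 is on the change-score SD, the adjusted effect is 0.5/√((1+ρ)/2). That is 0.577 at ρ = 0.5 and 0.513 at ρ = 0.9. With 125 df and alpha .05, power is 90% and 82%.

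**The case against.** The strongest reply is that these are two numbered comparisons, each reported on its own, in a small comparative trial that never declares one overall success criterion. On that reading 5% and 80% hold for each outcome. This stands, and it means that a family-wise error near 10% is not an established property of the plan: it follows only if either result may carry the Aim 1 conclusion. But the documents do not adopt the separate-claims reading either. They power one aim and answer it with both tests. Even as separate claims, the day and the tissue source remain open.

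It is also fair to say that a change-score t-test is valid under randomisation. Adjusting for Day 0 is therefore a gain in precision and not the repair of an error.

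Some stronger inferences are not supported:

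- **That 64 per arm is miscalculated.** It reproduces for one test.
- **That only biofilm has an open day, tissue being fixed at Day 8.** This rests on the table alone. The opening summary and the blinded photo ratings both provide a Day 4 tissue value.
- **That a third test should be counted because cultures are taken on two post days.** No section says biofilm will be tested on both.
- **That the PI's monthly data review invites choosing the outcome by its result.** The Data and Safety Monitoring Plan gives its purpose as finding breaches of protocol.

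**Conclusion.** The concern holds as a gap in specification. Aim 1 has no named primary outcome, no rule for combining its two tests, no post day for either outcome and no stated source for tissue. Three places disagree on when tissue is assessed: the opening summary, the photo-rating text and the data collection table.

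The numerical consequence is conditional. If the two tests are to support one conclusion on Aim 1, the plan gives either an error above 5% or power below 80%, within the ranges tabulated above. Those ranges rest on assumed correlations and, for power, on d = 0.50 for both outcomes. If the outcomes are separate claims, neither figure is affected and only the undefined day and source remain. The point should be settled before analysis. It does not call the sample-size arithmetic into question.

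**What to change.** **1. Specify Aim 1.** In Data Analysis, before outcome data are summarised by arm, name one primary outcome, one measurement source (for tissue, provider assessment or blinded photo rating) and one post day. Make the other outcome and the other day secondary. Reconcile the opening summary, the photo-rating text and the table on when tissue is assessed. Whichever day is chosen, state how it falls relative to sharp debridement in controls: four days after on Day 4, 24 hours after on Day 8. This takes a few sentences, uses data already planned, and keeps 64 per arm and 80% power. The price is that the other outcome loses confirmatory status.

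If both outcomes are to stay primary, state the rule and restate power at 64 per arm:

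- **Holm:** 71% per outcome at the .025 step. Restoring 80% at that level would need 78 per arm, or 156/0.9 ≈ 174 recruited at the plan's 10% attrition, against 140 now.
- **Both required:** each stays at .05, and the stated power becomes 64% to 75%.

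**2. Separately, adjust for baseline.** Replace the change-score t-tests with a comparison of the post value adjusted for the Day 0 value, on the same scale if a transformation is used. It needs no new data. Power at .05 would be about 82% to 90% for an assumed pre-post correlation of 0.9 down to 0.5, provided d = 0.50 refers to the change-score SD, which the plan does not say.
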